5.2. Exclusion Criteria

Subjects will be excluded from the study if they meet any of the following criteria:

- 1. Pregnant or breastfeeding or plan to become pregnant during the study.
- 2. Other than MDD (primary focus of treatment), having a current psychiatric disorder, such as personality disorder, schizophrenia, schizoaffective disorder, other psychotic disorder, bipolar disorder, eating disorder, dementia, fibromyalgia, intellectual disability, or mental disorder due to a general medical condition, as defined by DSM-5, or has been treated with ECT within 6 months prior to screening. Comorbid anxiety disorders are not exclusionary.

3. With the exception of caffeine dependence and mild to moderate nicotine dependence, have a positive urine drug screen (UDS) at screening or Day 1 for disallowed substances, including barbiturates, phencyclidine, cocaine, amphetamines, or a history of illicit drug or alcohol abuse within 1 year prior to screening judged by the investigator to be excessive or compulsive, or currently using drugs of abuse or any prescribed or over the-counter medication in a manner that the investigator considers indicative of abuse or dependence.

Note: Subjects testing positive for cannabinoids at screening may be eligible for participation in the study if all of the following criteria are met:

- The subject does not meet the diagnostic criteria for moderate or severe substance use disorder within the 6 months before screening based on the MINI
- Based on the investigator's clinical assessment, the subject's marijuana use is limited to ≤3 times per week and is not expected to interfere with their ability to adhere to study procedures
- Marijuana is legal per local law
- 4. Have a significant risk of suicidal or violent behavior. Subjects with any suicidal ideation of type 4 (active suicidal ideation with some intent to act, without specific plan) or type 5 (active suicidal ideation with specific plan and intent) or any suicidal behavior in the past 12 months before screening based on the C-SSRS or according to the investigator's clinical judgment should be excluded.
- 5. A history of seizure disorder, stroke, Alzheimer disease, Parkinson disease, multiple sclerosis, head injury associated with loss of consciousness for more than 15 minutes, or other neurodegenerative disorder.
- 6. Have a known or suspected diagnosis of Acquired Immune Deficiency Syndrome (AIDS).
- 7. Other clinically significant laboratory or vital sign abnormalities that are not attributed to a stable, well-controlled medical condition.
- 8. A clinically significant ECG abnormality confirmed by central rater at screening or prior to randomization confirmed by the site investigator.
- 9. An unstable medical condition or chronic disease (including history of neurological [including cognitive impairment, myasthenia gravis], hepatic, renal, cardiovascular, gastrointestinal, pulmonary, autoimmune, or endocrine disease that may affect study participation or results) within 3 months before Day 1, or malignancy within 6 months before Day 1, or any history of gallstones, endoscopic retrograde cholangio pancreatography or cholestasis.
- 10. QT interval corrected for heart rate using Fridericia's correction (QTcF) >450 msec (males) or >470 msec (females) either at screening (per central rater) or Day 1 (per investigator), confirmed with 1 repeat test; or the subject has long QT syndrome or is under the treatment with Class 1A (eg, quinidine, procainamide) or Class 3 (eg, amiodarone, sotalol) antiarrhythmic drugs.

- 11. Evidence of chronic renal or liver disease based on any of these screening laboratory test abnormalities:
 - Serum creatinine >1.5×upper limit of normal (ULN) for males and >1.2×ULN for females.
 - AST $>2\times ULN$.
 - ALT $>2 \times ULN$.
 - ALP >1.5×ULN.
 - GGT >2×ULN.
 - TBILI >1.5×ULN unless due to a documented diagnosis of Gilbert syndrome.
- 12. Have any of the following laboratory abnormalities at screening:
 - Prothrombin time (PT) expressed as international normalized ratio (INR) >1.3, unless the subject is on anticoagulant treatment that affects INR.
 - Hemoglobin <10 g/dL.
 - White blood cell (WBC) count $<3.0 \times 10^3/\text{mm}^3$.
 - Platelet count <100,000/mm³.
 - Absolute neutrophil count $<1.0 \times 10^3/\text{mm}^3$.
- 13. Are currently taking any of the prohibited medications listed in Section 7.1 Table 2. Subjects who have received these medications in the past must have been off them for at least 30 days prior to Day 1.
- 14. Have ingested grapefruit juice, grapefruit products, Seville oranges, or Seville orange products within 7 days before Day 1.
- 15. Used any active investigational drug in the context of a clinical study within 3 months before baseline or plans to use such an investigational drug (other than the study treatment) during the study.
- 16. Blood loss \geq 550 mL within 8 weeks before Day 1.
- 17. Has previously participated in this study, has participated in more than 2 investigational drug studies in the previous 12 months, is currently participating in another clinical study per subject registry database query, or has participated in a clinical study for a psychiatric condition that is exclusionary per this protocol. This criterion does not pertain to participation in an investigational vaccine clinical study, which is allowed if completed more than 30 days before screening. This criterion must be reconfirmed prior to the first dose of study treatment on Day 1.
- 18. In the investigator's opinion, the subject is not capable of adhering to the protocol requirements, or has a history of poor or suspected poor compliance in clinical research studies, or the subject has a history of poor or suspected poor compliance to antidepressant medication.

6. STUDY TREATMENT

6.1. General Information

Study treatments are summarized in Table 1.

Table 1: Study Treatments

Treatment Group	Active (NBI-1065846)	Placebo
Treatment administration	NBI-1065846 will be administered orally once weekly, at a loading dose of 160 mg on Day 1 followed by a once weekly 80 mg dose on Weeks 2 to 8.	Placebo tablets identical in appearance to the active product will be administered in the same manner and on an identical schedule as NBI-1065846
Unit dose strength	40 mg per tablet	Not applicable
Dose formulation	Tablet	Tablet
Route of administration	Oral	Oral
Sourcing	Provided centrally by Sponsor	Provided centrally by Sponsor
Packaging and labeling	Provided in HDPE bottles labeled in accordance with applicable regulatory requirements.	Provided in HDPE bottles labeled in accordance with applicable regulatory requirements.

HDPE=high density polyethylene

6.2. Study Treatment Administration

Study treatment will be administered orally once weekly (every 7 days \pm 2 days), with each dose taken at least 5 days apart. Subjects receive a loading dose of 160 mg (consisting of four 40 mg tablets) in the clinic on Day 1 (Week 1) and subsequently 80 mg (consisting of two 40 mg tablets) once weekly (Weeks 2 to 8) thereafter. Subjects will also receive their second (Day 8), and fifth (Day 29) doses of study treatment in the clinic. Subjects will take study treatment at home on Days 15, 22, 36, 43, and 50. Study treatment will be administered with 240 mL of water and may be administered with or without food.

If a subject forgets or is unable to take the study treatment, the dose can be taken ± 2 days from the scheduled weekly dose (with each dose taken at least 5 days apart); otherwise the study treatment should be taken at the next dosing time.

6.3. Study Treatment Compliance

At each onsite or virtual study visit (except the Day 1 visit), the investigator or designee will remind subjects to take their study medication on the next scheduled day as specified in Section 6.2. For weeks with no study visit scheduled, this reminder should occur via telephone. The subject should also be reminded that if they forget or are unable to take the study treatment,

the dose can be taken ± 2 days from the scheduled weekly dose (with each dose taken at least 5 days apart); otherwise the study treatment should be taken at the next dosing time.

A compliance check will be performed by counting the tablets of study treatment returned at each specified study visit; details are provided in Section 6.4. Assessment of study treatment compliance will be determined by the investigator at each visit based on all available information.

6.4. Study Treatment Storage/Compliance

The designated personnel are responsible for maintaining records of the quantity and dates of all study treatment supplies received, dispensed, returned, lost, and destroyed, according to applicable regulations and study procedures. Study treatment should be stored in a locked area accessible only to the designated pharmacist or qualified personnel. A detailed description of how study treatment should be dispensed, stored, and any stability changes will be provided in the Pharmacy Manual.

6.5. Study Treatment Accountability and Return

Subjects will bring all unused study treatment and empty packaging material to the center at specified study visits for study treatment accountability and reconciliation by study center personnel. A compliance check will be performed by counting the tablets returned at each on-site study visit.

The quantity of study treatment dispensed, used, and returned will be recorded on a dispensing log or otherwise documented. The quantity of study treatment lost or destroyed must also be accounted for and documented. The designated pharmacist or qualified personnel will be responsible for maintaining accurate records of the quantity and dates of all study treatment supplies received, dispensed, and returned.

If unused study treatment is not returned to the Sponsor or its designee, alternative disposition of study treatment must be documented and follow local laws and regulations.

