- ^h If a female of childbearing potential has an indeterminant β-hCG pregnancy test result, the test should be repeated during the screening period and the subject discussed with the medical monitor.
- ⁱ Only for postmenopausal women.
- Urine drug screen (UDS) will be analyzed at screening by the central lab. A UDS kit provided by the central laboratory will be used at the site to confirm eligibility on Day 1. Drug/alcohol screening may be repeated at any

time per the investigator's clinical judgment. Any positive UDSs during conduct of the study must be discussed with the Sponsor or designee to determine the subject's disposition.

k A trained rater will read the PCRS to the subject prior to administration of the efficacy rating assessments. After administering the PCRS, the efficacy assessments should be performed in the following order throughout the study: SHAPS (at screening and baseline only), DARS,

MADRS, HAM-D17 (at screening and baseline only), CGI-S,

- .
- ^m If the subject discontinues study treatment, a blood sample for PK is needed at any time during early ET visit.
- ⁿ One bottle will be dispensed to the site at Baseline/Day 1 and will remain in the clinic for onsite subject dosing (ie, on Days 1, 8, and 29). A second bottle will be dispensed to the subject at Day 8 to take home for at-home dosing (ie, on Days 15, 22, 36, 43, and 50).
- Ocllect any remaining study treatment from the subject at Day 57 or ET visit if the subject discontinues study treatment.
- P Each dose of study treatment should be taken at least 5 days apart. Onsite dosing in the clinic will occur on Day 1, Day 8, and Day 29. Subjects should hold morning study treatment dose until instructed to take at the study site in order to collect predose PK blood samples. Subjects will take study treatment at home on Days 15, 22, 36, 43, and 50. At each onsite or virtual study visit (except the Day 1 visit), the investigator or designee will remind subjects to take their study medication on the next scheduled day. For weeks with no study visit scheduled, this reminder should occur via telephone. The subject should also be reminded that if they forget or are unable to take the study treatment, the dose can be taken ± 2 days from the scheduled weekly dose (with each dose taken at least 5 days apart); otherwise the study treatment should be taken at the next dosing time.
- ^q A compliance check will be performed by counting the tablets returned at each on-site study visit.

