9.1. Study Treatment Dosing and Compliance

The duration of exposure to randomized study treatment will be calculated as: last dose date – first dose date +1.

Duration of exposure will be summarized with descriptive statistics by treatment group.

The percentage of study drug compliance will be defined as (number of tablets dispensed – number of tablets returned) / 8 x 100%.

Assessment of compliance will be summarized as number and percentage of subjects receiving <80%, 80%-120%, and >120% of prescribed study treatment.

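### SAP 9.1 counts tablets documented as lost, and tablets in an unreturned take-home bottle if scored as zero returned, as taken, so the compliance table can miss under-dosing (minor)

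*Protocol*

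**What the plan says.** SAP 9.1 gives the rule: "The percentage of study drug compliance will be defined as (number of tablets dispensed – number of tablets returned"), divided by 8 and expressed as a percentage. The result is then banded: "Assessment of compliance will be summarized as number and percentage of subjects receiving <80%, 80%-120%, and >120% of prescribed study treatment". The formula has no term for tablets used, lost or destroyed, and the SAP has no rule for a bottle that is not brought back.

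The protocol collects more than this. Section 6.4 requires records of lost and destroyed supplies as well as those dispensed and returned. Section 6.5 has the quantity used entered in a dispensing log or documented in another way, and continues: "The quantity of study treatment lost or destroyed must also be accounted for and documented". Section 6.3 says: "Assessment of study treatment compliance will be determined by the investigator at each visit based on all available information".

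On supply, footnote n to Table 8 (Appendix A) keeps one bottle at the site for the Day 1, 8 and 29 doses. For the other five doses, "A second bottle will be dispensed to the subject at Day 8 to take home for at-home dosing". Footnote o has any remaining tablets collected from the subject at Day 57 or the ET visit.

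**The concern.** A numerator of dispensed minus returned assumes that whatever did not come back was swallowed. For a tablet recorded as lost, the study's own log contradicts that assumption. For a bottle that never comes back, nothing supports it.

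The supply scheme makes this matter more than usual. All five home doses are handed out at once on Day 8, so a subject who stops soon afterwards and does not return the bottle can be credited with the whole home course. Early stoppers with low intake are the subjects that the '<80%' row exists to show. If they cannot appear there, the table is of little help when a weak DARS result or an adverse event rate has to be read against the drug actually taken.

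**Working it through.** **Inputs**

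- First dose: "Subjects receive a loading dose of 160 mg (consisting of four 40 mg tablets) in the clinic on Day 1 (Week 1"), so 4 tablets (Protocol 6.2).
- Later doses: "80 mg (consisting of two 40 mg tablets) once weekly (Weeks 2 to 8) thereafter", so 7 × 2 = 14 tablets (Protocol 6.2).
- Full course: 4 + 14 = 18 tablets in 1 + 7 = 8 weekly doses.
- Clinic bottle (Days 1, 8, 29): 4 + 2 + 2 = 8 tablets. Take-home bottle (Days 15, 22, 36, 43, 50): 5 × 2 = 10 tablets (Table 8, footnote n).
- SAP formula: "number of tablets dispensed – number of tablets returned) / 8 x 100".

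**The plan's own figure.** The divisor of 8 is the number of weekly doses, not the number of tablets in a course. It also happens to equal the clinic-bottle count. A fully adherent subject scores 18 / 8 = 225%. This unit mismatch is a separate and larger error, so each result below is shown with both divisors.

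**Case 1: documented loss.** Take a subject who attends throughout, loses 4 take-home tablets (two doses) that are recorded as lost and not replaced, and takes the rest.

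- True intake: (18 − 4) / 18 = 77.8%, which belongs in '<80%'.
- Numerator under the SAP: 18 − 0 = 18. Score: 18 / 8 = 225%, or 18 / 18 = 100% with the divisor corrected.

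This case needs no assumption about unreturned bottles.

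**Case 2: take-home bottle not returned.** Assumptions: bottles hold exactly the scheduled tablets, unused clinic tablets count as returned, and an unreturned bottle counts as zero returned. True intake is measured against the full course, as the SAP's fixed divisor implies. The numerator is clinic tablets taken plus 10.

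| Last dose | Taken | True % (of 18) | SAP numerator | SAP score (/ 8) | Score with / 18 |
|---|---|---|---|---|---|
| Day 8 | 6 | 33.3 | 6 + 10 = 16 | 200% | 88.9% |
| Day 15 | 8 | 44.4 | 16 | 200% | 88.9% |
| Day 22 | 10 | 55.6 | 16 | 200% | 88.9% |
| Day 29 | 12 | 66.7 | 8 + 10 = 18 | 225% | 100% |
| Day 36 | 14 | 77.8 | 18 | 225% | 100% |
| Day 43 | 16 | 88.9 | 18 | 225% | 100% |
| Day 50 | 18 | 100 | 18 | 225% | 100% |

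The first five rows belong in '<80%'. None lands there: all are in '>120%' with the SAP's divisor and in '80%-120%' with 18. If both counts are instead converted to doses, the scores are 7 / 8 = 87.5% (last dose Day 8 to 22) and 8 / 8 = 100% (Day 29 or later), again never below 80%. A subject who stops after Day 1 has no take-home bottle and is placed correctly: 4 / 8 = 50%, or 4 / 18 = 22.2%.

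**Sensitivity to bottle fill, which is not stated.** With 2 spare tablets in the take-home bottle the scores are 225% to 250% (/ 8) and 100% to 111.1% (/ 18). With 10 spare they are 325% to 350% and 144.4% to 155.6%. The band under / 18 changes, but no score drops below 80%.

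**Why both parts of the ratio need correcting.** Changing only the numerator leaves full adherence at 225%. Changing only the divisor moves the five early-stopping rows from '>120%' into the normal band, where they are harder to notice.

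**The case against.** The case on the other side is substantial.

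- *These subjects are not shown as compliant.* A reader might infer that dropouts who keep the bottle are tabulated in the '80%-120%' band. With the SAP's divisor they are not: they score 200% to 225% and sit in '>120%', as do fully adherent subjects. The '80%-120%' result appears only with a tablet or dose conversion that the SAP does not contain, and with little bottle overage. What stands is that they never reach '<80%' and cannot be told apart from full adherence.
- *Zero returned is an assumption.* SAP 5.1 generally rules out replacing missing values, and SAP 9 summarises safety data as observed without imputation. An absent return count could equally make compliance missing. Case 2 is therefore conditional; Case 1 is not.
- *Under-dosing remains visible elsewhere.* SAP 9.1 also summarises exposure as last dose date minus first dose date plus 1, so a subject whose last dose was on Day 8 shows 8 days whatever became of the bottle. SAP 6.1 tabulates premature discontinuation with reasons, and SAP 8.1 summarises plasma concentrations by visit. This stands for early stopping. Exposure duration would not show doses missed within the interval because tablets were lost.
- *No efficacy result depends on it.* The Full Analysis Set ignores compliance, the estimand uses a treatment policy strategy, and no per-protocol set is defined. This stands in full.
- *The tablet count follows the protocol's own check*, which counts returned tablets. That is true of the check in Protocol 6.3 and 6.5, but 6.3 then widens the basis to all information available, and 6.5 requires the quantities that the SAP leaves out.

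**Conclusion.** The point holds in a limited form. SAP 9.1 states a numerator that scores documented losses as intake, against records that Protocol 6.4 and 6.5 require. If, in addition, an unreturned take-home bottle is read as zero returned, a subject with a last dose on Day 8 to Day 36 never falls in '<80%', whichever divisor is used.

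The number of subjects affected cannot be derived. A reader might take the planned 15% non-completion (0.15 × 88 = 13.2, about 13 subjects) as the pool. That rate concerns the Day 57 assessment, not treatment stopping or bottle loss. Subjects who stop treatment are meant to stay in the study (Protocol 8.1), remaining tablets are collected at Day 57 or ET, and only last doses from Day 8 to Day 36 produce the misclassification. The documents give no bottle non-return rate.

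The effect is confined to one descriptive table. Severity: minor.

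**What to change.** Amend SAP 9.1 in one step with the divisor:

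- **Divisor:** prescribed tablets for the course (18 on the documented schedule) in place of 8.
- **Numerator:** tablets recorded as used; or dispensed minus returned minus tablets lost or destroyed before return. Tablets that were returned and later destroyed must not be subtracted a second time.
- **Unreturned take-home bottle with no recorded quantity used:** report in a separate 'compliance unknown' row. The weekly reminder contacts should not be used to fill the gap, because the protocol describes them as reminders of the next dose and does not say that past doses are confirmed or recorded.

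With tablets used over 18, last doses on Day 8, 15, 22, 29 and 36 give 33.3%, 44.4%, 55.6%, 66.7% and 77.8%, all in '<80%'. Day 43 gives 88.9% and Day 50 gives 100%.

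The cost is a few lines in SAP 9.1, one extra table row and a small programming change. The quantities are already required by the protocol, so no new data collection is needed. Where a bottle is not seen again and no use was recorded, compliance stays unknown, and the table should say so.

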6.6. Direct-to-Subject Shipments of Study Treatment

To ensure continued access to study treatment, if a subject is unable to go to the site when study treatment is to be dispensed, study treatment may be delivered to the subject's residence by a distributor independent from the Sponsor. The subject's name, address, and other contact details will not be accessible to the Sponsor, and the distributor will not have access to the subject's health information.

6.7. Blinding

This is a double-blind, placebo-controlled study during which the subject, investigator, all study center personnel, pharmacist, and the Sponsor, with the exception of clinical study material supply chain personnel who are not involved in decisions regarding subject's study treatment, will be blinded to the subject's study treatment assignment (NBI-1065846 or placebo).

The randomization code will be broken for an individual subject only if the subject is pregnant, experiences an SAE that the investigator feels cannot be adequately treated without knowing the subject's study treatment assignment, or for regulatory reporting requirements. In the case of a medical emergency in which knowledge of the identity of the study treatment is important for subject management, the investigator has the responsibility to decide whether to break the blind; study treatment assignments would be unblinded using interactive web response system (IWRS). It is recommended that the investigator contact the Study Medical Monitor (or designee) before unblinding if it would not result in unnecessary delay to the immediate medical management of the subject. The investigator must document the date, time, and the reason the blind was broken.

6.8. Procedures for Overdose

Any dose of study treatment administered in excess of the protocol-specified dose will be considered an overdose.

In the event of a suspected overdose, the investigator and/or treating physician should:

- 1. Closely monitor the subject for any AE/SAE and laboratory abnormalities and follow the AE reporting process. The Study Medical Monitor should be contacted for AEs related to an overdose.
- 2. Document the total quantity of the excess dose(s) as well as the date(s) on which additional dose(s) were taken, if this information is available.

Subjects who overdose will be counseled on correct dosing and administration of study treatment, as necessary. Decisions regarding study discontinuation, dose interruptions, or dose modifications will be made by the investigator in consultation with the Study Medical Monitor based on the clinical evaluation of the subject.

